##### Exclusion criteria:

Individuals not meeting the above criteria or meeting any of the following criteria will be excluded:

- Concurrent enrolment in another HIV-1 vaccine or prevention trial**
- Medical hospitalization in the past year, for reasons not associated with obstetric health (e.g. c-section, miscarriage, pre-eclampsia)**
- Active TB or receipt of TB treatment within the past 30 days**
- History of renal disease**
- Current clinical diagnosis of hypertension**
- Exhibiting psychotic symptoms (including hallucinations, suicidal or homicidal ideations, or violent behaviour)**
- Currently or history of taking an anti-psychotic medication (such as for treatment of bipolar disorder, schizophrenia, or postpartum psychosis following a previous pregnancy)**
- Positive Hepatitis B surface antigen (HBsAg) test on screening**
- History of bone fracture not related to trauma**

- Any other medical, psychiatric or social condition which in the opinion of the investigators would affect the ability to consent and/or participate in the study.

Study censorship will include:

1. Seroconversion
2. Moves away
3. Transfers out of care
4. Lost to follow up (e.g. does not return for study or clinical visit for >8 weeks and study staff are unable to track the participant, or she does not want to continue in the study).

Eligible, consenting women will receive up to R250 in grocery vouchers, transportation and refreshments per visit for their time and effort in the study as well as transportation to the facility. All participants will also receive minor refreshments (e.g. sandwich and cool drink) on the day of their visit.

Procedures for the informed consent process are outlined below. Throughout, trained study staff will ensure that women are aware of their right to refuse and/or withdraw from the study at any time. In addition, study staff will emphasize that all study activities are entirely separate from routine ANC and postnatal care services received and that refusal or withdrawal from the study will have no impact on their ability to access any services provided at any public-sector health facility.

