## **5. Study procedures**

The study will be integrated into the MOUs. Women will be recruited directly from antenatal care. We will train existing counsellors, nurses and midwives in PrEP treatment (including risks and benefits) and the study. A trained recruiter will recruit directly from women at their first ANC visit, and if interested and eligible after the screening process, the women will go to the study space (Hanover Park) or study trailer (Green Clinic) in Gugulethu for the consent and study enrolment procedures. Consented, enrolled women will be invited to return every 3 months for study visits that correspond with their next ANC visit. All study staff will be trained, salaried staff working for UCT.

The purpose of the study visits will be to evaluate the study objectives. Below are the detailed steps for patient recruitment, enrolment, consent and study participation (Figure 5).

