**Step 12:** The participant will receive a snack and reimbursement for her time and transportation (up to R250 in a Shoprite voucher, refreshment and reimbursement for transportation) which is in line with our ongoing research at these sites. Further, we will combine the study visits with existing ANC or post-partum/well-baby visits to minimize the travel to the facilities outside of normal clinical checkups.

2. For follow up return visits:

Follow up visits will be at 1 month after baseline (to coincide with ANC visits) then after two months after birth then every 3 months thereafter (to coincide with post-partum, well-baby visits).

COVID update: During the COVID-19 lockdown, we will offer women the option of participating in interviews over the phone with participants who are willing and unable to attend the study visit. The interviewer will be in a private room and will ask the participant to be in a private, quiet space. The interviewer is an experienced isiXhosa -speaking research assistant and interviews will be conducted over the phone while the interviewer collects the data on the tablet using RedCap. Updated processes include:

- **Calling participants who miss study visits to assess if they wish to participate a phone interview (and schedule a time when they can be alone in a quiet place for 20-30 minutes)**

The interviewer will ascertain the participant ID and date of birth to ensure that they are speaking with the participant.

**Step 1:** In ANC: Healthcare providers provide counseling on HIV prevention and treatment at each ANC visit including HIV testing, as part of standard of care. In post-natal care and well-baby visits women may not receive regular HIV testing and messages and will receive this within step 2 (with study counselor). Following their ANC visit, enrolled women will be invited to attend the study site in each MOU to do the follow-up visit including the survey and prescription and adherence counseling (if on PrEP).

**Step 2:** Survey at each visit in a private study room

**Step 3:** In the study room, the study counselors will provide PrEP-specific counseling including adherence counseling for those on PrEP (and management of side effects), or counseling about the risks and benefits of PrEP for women not yet on PrEP. Women not on PrEP will be asked if they are interested in starting PrEP at this visit.

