**Step 4:** *For participants on PrEP*, the study nurse performs a blood draw for creatinine clearance and a finger prick for DBS testing for adherence measures and (if applicable for this visit). See Table 1 for study calendar.

**Step 5 (for women on PrEP):** At each visit the study counselor will ask, and record responses, all participants on PrEP about any side effects associated with TDF/FTC, including diarrhea, nausea, fatigue, headache and rash (which are seen in about 10% of participants during the initiation of therapy). We will encourage participants to contact the study nurse if they experience side effects between visits.

**PrEP retention methods to improve adherence:** Each study visit will include counselling from peer counsellors who will discuss the importance of retention and adherence to PrEP for effectiveness. We will adapt messages from ongoing PrEP studies conducted by co-I [name] and team. We will also provide participants with a brochure to take home that discusses retention, adherence and side effects of PrEP. Each visit will include group and individual counselling. Group counselling will be led by a mother who has successfully taken PrEP for 3+ months to guide a discussion about the importance of retention, reminders on how to take the medication daily and how to address side-effects (e.g. nausea, headaches, etc).

**Step 6:** PrEP provision (for 1 or 2 months) and appointment reminder

*Follow-up & retention:* Tracing information will be taken at the enrolment visit and updated at each study visit. Retention activities will focus on scheduled measurement visits. Following our established approach in this

setting, we will provide reminder calls to participants before their measurement visits, and initiate tracing, including home visits, for women who do not attend the measurement visit within one week of the scheduled visit.

*PrEP provision:* monthly for the first 3 months, and then 2-months intervals after that. Participants on PrEP will have regular monitoring with laboratory tests, including creatinine levels to check for changes in renal function and dried blood spots (DBS) for adherence measures. Those with HBsAg+ will be excluded from the study. We will test for HIV seroconversion at every study visit.

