**Table 1. Study measures for PrEP-PP for AIM 1**

Primary Outcomes	Measurement	Source	Frequency
PrEP initiation	# of women who initiate PrEP over time / total # of women in active cohort = proportion of women who initiate PrEP	Electronic provider log (REDCap)	Quarterly
PrEP continuation	# of women on PrEP who return for study visits (do not miss more than 1 visit) / total # of women in active cohort who are prescribed PrEP= proportion of women on PrEP who continue in PrEP study	Electronic provider log (REDCap)	Quarterly
PrEP persistence (subjective)	# of women reporting taking PrEP in $\geq 5$ out of last 7 days or $\geq 25$ out of last 30 days (self-reported)/ total woman-time on PrEP in active cohort = PrEP persistence rate (subjective)	Electronic provider log (REDCap)	Quarterly
PrEP persistence (objective)	# of women taking PrEP who have $\geq 600$ fmol/punch (~7 doses/week) from DBS TDF-DP at 3rd trimester, delivery, and 6 weeks postpartum (and during sexual risk periods during that time) / total woman-time on PrEP in active cohort = PrEP persistence rate (objective)	Lab analysis of TDF-DP measures	Yearly and end of study
Secondary Outcomes			
Prevention effective persistence	4. # of women reporting adherence to PrEP (as per PrEP persistence subjective measure)/ total woman-time reporting sexual activity in past 30 days	Electronic provider log (REDCap)	Quarterly
	5. # of women having TDF-DP in DBS (as per PrEP persistence objective measure)/ total woman-time reporting sexual activity in past 30 days	Lab analysis of TDF-DP measures	Yearly and end of study

Prevention effective continuation	# of women who don't miss any PrEP study visits/ total woman time reporting sexual activity in prior visit	Electronic provider log (REDCap)	Quarterly
Predictors of attrition at key steps in the PrEP cascade	Individual, pill/study and disease specific predictors of PrEP initiation, continuation and persistence	Study CRFs and in-depth interviews (month 7 and12) (mixed methods)	End of study
Healthcare provider attitudes and knowledge about PrEP in pregnancy	Provider knowledge about PrEP and barriers/facilitators to PrEP prescription in ante and postnatal care	In-depth interviews	Year 1 of study
HIV outcomes	HIV testing data: HIV-uninfected, HIV incidence in mother and child (if mother seroconverts) compared by PrEP use/non-use	Electronic provider log (REDCap)	End of study

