#### Birth outcomes

	PrEP user (n)	%	PrEP non-user (n)	%	Comment
Number of active participants					
Number of women still pregnant					
Number of Births					
Number of Live Births					
Number of Birth abnormalities					
Still births					
Miscarriage					
Other					

Monthly and quarterly report templates (can be by PrEP status for our DSMB and other analyses)

Table 1: Monthly enrolment information for participants

Description	N for this month	% for this month	Cum. total (for study)	% Cum. total	Comments
Enrolment Status					
Total Screened					
Ineligible					
Refusals					
Enrolled participants					
Withdrawals (total N=X)					
Study withdrawals					Monthly PIDs:
Censored from study					
Lost to follow up (90+ days without a visit and not contactable)					
Total					
PrEP Status of Study participants (total N=X)					
On PrEP ( $\geq 18$ yrs)					

On PrEP (16-17 yrs)					
Not on PrEP (18 $\geq$ yrs)					
Not on PrEP (16-17 yrs)					
Total					
Visit attendance					
Attended Refill visit (v1.1)					
Attended v2					
Not on PrEP (v2- subset of above row)					
AE and SAE reporting					
AEs reported ( $\geq$ 18 yrs)					
AEs resolved ( $\geq$ 18 yrs)					
AEs reported (16-17 yrs)					
AEs resolved (16-17 yrs)					
SAEs (denominator= total enrolments)					
Birth outcomes					
Normal					
Adverse (& reason)					
Total births					
STI diagnosis					
CT					
NG					
TV					
CT/NG					
CT/TV					
TV/NG					
CT/NG/TV					
Total					
Referrals					

IPV					
EPDS (depression)					
AUDIT					
DUDIT					
HIV results at Baseline					
HIV negative					
Ag					
Ab					
Ag/Ab					
Total Tested Participants					
HIV results at visit 2+					
HIV negative					
Ag					
Ab					
Ag/Ab					
Total tested					

Abnormal laboratory results (creatinine)	
Unanticipated problems	
Protocol Deviations	
Quality Management	

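### An untraceable PrEP initiator can be classed as lost before she can count as a non-continuer, and the undefined active-cohort denominator then lets her drop out of the continuation proportion

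*Combined protocol and SAP*

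**What the plan says.** **Loss to follow-up.** Protocol section 4, after the exclusion criteria, introduces a list with "Study censorship will include". One entry is loss to follow-up, where a woman "does not return for study or clinical visit for >8 weeks and study staff are unable to track the participant" or does not want to continue. The monthly enrolment report template in SAP section 4 has a row reading "Lost to follow up (90+ days without a visit and not contactable", placed under withdrawals. Neither rule states the day from which time is counted.

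**Visit schedule.** Protocol section 5 says women are "invited to return every 3 months for study visits". Its follow-up paragraph differs: "Follow up visits will be at 1 month after baseline", then two months after birth, then three-monthly. PrEP provision is "monthly for the first 3 months, and then 2-months intervals after that". The shell for Table 2 in SAP section 4 lists return visits at 1 and 3 months and then every 3 months to month 18.

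**Continuation.** The SAP's study measures and its Table 1 count women on PrEP who have not missed more than one visit. The denominator is "total # of women in active cohort who are prescribed PrEP". The active cohort is not defined. Protocol Table 2 uses the same ratio under the name retention. The Aim 1 objectives in SAP section 1 give another definition: a refill within 45 days of initiation.

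**Analysis.** The SAP's sample size section and section 2.4 base the analysis on women who complete 12-month postpartum follow-up. The SAP's modelling text also plans a time-to-event analysis of loss among initiators, which it equates with non-continuation. It further plans inverse probability of censoring weighting and multiple imputation as bias analyses.

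**The concern.** Continuation is a primary outcome and feeds the Aim 3 model. It is a ratio whose failures are women who stop returning. If a woman who stops returning is first reclassified as lost, and lost women are not part of the active cohort, she leaves the denominator and never enters the ratio as a failure. The proportion then partly measures how quickly staff close a file. The protocol labels loss as censoring while the SAP's time-to-event analysis treats it as the event, so two analysts could code the same woman in opposite ways and both claim to follow the plan.

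**Working it through.** **1. The plan's own figures.** SAP section 2.2: 1200 × 0.60 = 720 initiators; 720 × 0.75 = 540 continuing at 12 months; 540 × 0.70 = 378 adherent. All three reproduce. Expected non-continuers: 720 − 540 = 180.

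**2. Time to each classification.** 8 weeks = 56 days. One quarter = 365.25/4 = 91.3 days (three calendar months span 89 to 92 days). Missing more than one visit means missing two, so the earliest failure is 2 × 91.3 = 182.6 days after the last attended quarterly visit. The documents give several schedules and no clock start, so the comparison is shown for each (days after the last attended visit):

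| Schedule and clock start | Second missed visit | 8-week rule | 90-day rule |
|---|---|---|---|
| Quarterly, from last visit | 182.6 | 56 | 90 |
| Quarterly, from first missed visit | 182.6 | 91.3 + 56 = 147.3 | 91.3 + 90 = 181.3 |
| Two-monthly refills, from last visit | 365.25/3 = 121.8 | 56 | 90 |
| Monthly refills, from last visit | 365.25/6 = 60.9 | 56 | 90 (later) |

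The 8-week rule precedes the second missed visit in every row. The 90-day rule precedes it clearly in the first and third rows, by about a day in the second, and not in the fourth.

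**3. Adding the tracing condition.** Protocol section 5 starts tracing when a woman has not attended within one week of a scheduled visit: 91.3 + 7 = 98.3 days on the quarterly schedule. Counted from the last visit, both thresholds have then passed, unless a clinical visit has reset the protocol's clock. Failed tracing alone would then class her as lost, as early as 182.6 − 98.3 = 84.3 days before she could miss a second visit.

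**4. Whether a lost woman leaves the ratio.** No sentence says so directly. Four features point that way: loss is listed as censorship in the protocol; the template places it under withdrawals; the denominator is the active cohort; and the analysis is based on completers. No passage states that lost initiators stay in the continuation denominator.

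**5. Size, for illustration only.** Let f be the share of the 180 non-continuers removed as lost. The documents give no value for f. Reported continuation = 540 / (720 − 180f):

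- f = 0: 540/720 = 75.0%
- f = 0.25: 540/675 = 80.0%
- f = 0.50: 540/630 = 85.7%

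With all 720 initiators kept and loss counted as failure, the result is 75.0% whatever f is.

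**The case against.** Several points on the other side stand.

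- A reader might infer that both thresholds are shorter than one quarterly interval. That holds for 8 weeks but not clearly for 90 days, which is about one interval (89 to 92 days). The relevant comparison is with two intervals.
- A reader might infer that an on-schedule woman could be classed as lost between visits. Both rules normally also require failed contact, tracing normally follows a missed visit, and clinical visits reset the protocol's clock.
- The 90-day rule is a report-template row, separate from the row for women censored from the study. The template is labelled for other analyses as well as for the DSMB, but it does not set a censoring date. The thresholds differ by 90 − 56 = 34 days. It does not follow that each lost woman's person-time differs by 34 days, because neither document says person-time runs to the threshold.
- The SAP already treats loss among initiators as the event in the time-to-event analysis, calls early losses highly informative, and compares retained numbers with 540 of 720 initiators. This shows that the authors saw the issue. It does not settle the primary proportion, and it contradicts the protocol's censoring label. Weighting is offered only as a bias analysis. It lets women still observed stand in for lost women, which is unsuitable if loss is itself non-continuation.
- The 45-day refill definition is unaffected, since a woman fails it before either threshold. But SAP section 2.4 refers to Table 1 for the precise definitions, and Table 1 is visit-based.
- It would go too far to say that failed tracing picks out exactly the women who stopped PrEP. Some may have moved or obtained PrEP elsewhere.

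**Conclusion.** The concern holds in this form: under the visit-based definition, the plan as written allows untraceable initiators to be removed from the continuation proportion before they can count against it. The two loss rules disagree, and neither has a start point. The bias is upward provided that the women removed would have gone on to miss a second visit.

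The conclusion rests on two readings that the documents permit but do not state: that the clock runs from the last attended visit, and that a lost woman is no longer in the active cohort. The completers-only statement in the SAP would exclude lost women whichever threshold applies. The figures of 80% and 86% rest on assumed loss shares of 25% and 50% and on the planning value of 75%. A reader could extend the formula to a reported 100%, but that would require every non-continuer to be untraceable, which nothing in the documents supports. This should be corrected before the continuation analysis is run.

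**What to change.** 1. Use one loss-to-follow-up definition in the protocol, the SAP and the report template, with a stated start point. Lengthening the threshold to just over one visit interval would not be enough, because it could still fall well before the second missed visit.
2. Define the continuation denominator as all women who initiated PrEP, in place of the active cohort or the completers.
3. Count loss to follow-up among initiators as non-continuation in both the proportion and the time-to-event analysis, with one event date stated in advance (for example the first missed visit). Amend the protocol's censorship list so that it does not contradict this.
4. Reconcile the 45-day refill definition with the visit-based one, and name which is primary.
5. Reconcile the visit and provision schedules in protocol section 5, and say which contacts count as visits for this outcome.

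The cost is wording only, with no new data. The continuation figure will be less favourable, and because some lost women may have continued PrEP elsewhere, it may understate actual use. The report should say so.

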## Part 2: Baseline Characteristics

**Table 2: Baseline Demographic Characteristics (can be by PrEP status in analysis)**

Variable	Total	Percentage	Comments
Age (Years)			

16-17			
18-24			
25 and older			
Mean (SD)			
Median (IQR)			
Gestational age (Weeks)			
Mean (SD)			
Median (IQR)			
Education			
None			
Primary (Grade 1-7)			
Secondary lower (8-10)			
Secondary upper (11-12)			
Tertiary (attended / completed)			
Income			
Yes			
No			
Income Monthly (Rands)			
1 – 1 000			
1 001 – 5 000			
>5 000			
Total			
Main Sexual Partner			
No			
Yes			
Relationship status (of those with main partner)			
Married, living together			
Married, Not living together			

Not Married, living together			
Not Married, not living together			
Total			
Do you have other sexual partners (concurrent sex partners)			
No			
Yes			
Has your current main partner(s) ever been tested for HIV?			
Yes			
No			
I don't know			
N/A			
Total			
Partner HIV status (of those previously tested)			
HIV positive			
HIV negative			
Total			
PrEP Knowledge			
Never heard about it			
Heard about it before this study			

### Part 3: PrEP persistence and side effects

#### PrEP persistence and side effects at the refill visit (v1.1) and V2+

	V1.1	V2	V3	V4	V5
Taken PrEP in the last 30 days	N, %				
Yes					
No					
Had symptoms or side effects while on PrEP					
Yes					
No					

In the last 30 days, on how many days did you miss at least one dose of any of your PrEP					
Never missed (0 days)					
1 - 5 days					
6-10 days					
11-20 days					
>20 days					
In the last 7 days, on how many days did you miss at least one dose					
Never missed (0 days)					
1-3					
4-7					

#### Part 4: Birth outcomes (by PrEP status for analysis)

	Frequency	Percentage	Comment
Number of active participants			
Number of women still pregnant			
Number of Births, (n=X)			
Number of Live Births			
Number of Birth abnormalities			
Still births			
Miscarriage			
Other			

#### Part 5: Participants Visit

	Frequencies	Percentage
Refill visit		
Actual attended		
Missed visits		

Total		
Visit 2		
Actual attended		
Missed visits		
Total		

**Part 6: Expected vs achieved participants for enrolment (weekly, monthly and quarterly)**

	Expected	Actual	% achieved
Week 1			
Week 2			
Week 3			
Week 4			
Total
